## Abstract

The injection of BOTOX into peripheral muscles has been shown to have therapeutic effects in a growing number of indications including disorders involving skeletal muscle (e.g., strabismus, blepharospasm, cervical dystonia, spasticity, cosmetic), smooth muscle (e.g., bladder), glands (axillary hyperhidrosis) and nociceptive pain (e.g. migraine) (Brin. 2014). The mechanism of action on peripheral muscle is established, and the effects on peripheral sensory nociceptors continue under active investigation (Burstein et al., 2014; Zhang et al., 2016). Recently, several studies have suggested that peripheral BOTOX injections in the region of the glabellar lines (corrugator and proceris muscles) may be effective in treating major depression. In addition, peripheral cranio-facial injections have been found effective in treating chronic migraine (Whitcup et al, 2014). It is established that peripheral interventions can modulate functional CNS connectivity in motor and sensory disorders (Cook et al., 2014; DeGiorgio et al., 2013). In addition, functional imaging has demonstrated that modifying eyebrow height or corrugator contraction activity can have functional changes at the level of the amygdala (Heller et al., 2011; 2014; Hennenlotter et al., 2009; Kim et al., 2014). The mechanism underlying the effect of peripheral BOTOX injections on afferent systems is not well understood. Nevertheless, brainstem pathways are integral in this setting as the VIIth cranial nerve provides efferent innervation to the target muscles and sensation is mediated by the Vth cranial nerve. We propose to further explore the functional effects of BOTOX injections on brain in healthy controls. Our approach will involve the measurement of brain metabolites (precursors of metabolism) in the brainstem using MRS as well as functional connectivity (resting state MRI) and functional activation from sensory motor tasks using high resolution fMRI. Examining fMRI of the brainstem and the functional connectivity of the brainstem and connections to cortex, may provide additional insight into the effects of BOTOX on neurologic and psychiatric disorders.

## Overview of fMRI

Functional MRI (fMRI) allows the non-invasive visualization and mapping of human brain function (Friston et al., 1999, Francis et al., 2000, Jancke et al., 2000, Muller et al., 2009). Neural activity in functioning areas of the brain reduces local oxygen concentration, resulting in subsequent increase in blood flow (to replenish the cells with oxygen). This oxygenated blood creates a blood oxygen level dependence (BOLD) effect on the MR signal. By this BOLD effect, one can indirectly detect where cerebral metabolism is taking place.

There are few fMRI studies investigating the effects of BOTOX that have demonstrated relationships between facial feedback and emotional stimuli in the amygdala (Kim et al. 2014, Hennenlotter et al. 2008). These results suggest that motor input from facial expressions plays a role in perception of emotion. In fact, there are numerous current theories that peripheral motor function is intrinsic to all cognitive processing. By modulating peripheral input into the brainstem by relaxing facial muscles innervated by the brainstem nuclei, it is possible that reduced tonic activation (from the facial muscles) will affect other neural network thresholds as well, promoting functional plasticity, and leading to quantifiable differences in the fMRI signal.

## Overview of MRS

Magnetic resonance imaging spectroscopy (MSI/MRS) is used to quantify the level of various metabolites (intermediary and byproducts of metabolism) in the brain. Many of these metabolites can be measured using conventional proton ( $^1\text{H}$ ) imaging or with specialized Phosphorous ( $^{31}\text{P}$ ) techniques. MRS yields data from an arbitrary-sized voxel in the form of a spectrum, from which metabolic concentrations can be determined (Figure 1). These concentrations can then be compared across groups or related to individual differences in behavior, treatment response, etc.

For example, a number of metabolites *index neural activity and can be used to dissociate excitatory from inhibitory activity*. Total Creatine (**tCr**) signal in MRS is a combination of both phosphocreatine (**PCr**) and creatine (**Cr**). Both act as ATP regulators and their concentration in the brain is reflective of the high-energy phosphate buffer system. Glutamate (**Glu**) is the most abundant metabolite in the brain and a dominant excitatory neurotransmitter, released during neuronal excitation and converted to Glutamine (**Gln**). The Glutamate-Glutamine cycle is highly energy demanding and readily observed. **GABA** is the most important inhibitory neurotransmitter in the brain and, while more difficult to measure with MRS, can be accurately quantified with specialized protocols. **GABA** levels have been shown to change during motor learning (Floyer-Lee et al, 2006). In addition, elevated **GABA** levels have been detected in migraine (Aguila et al. 2015), and depression (Licata et al. 2014) making this metabolite well suited for this work.

Other metabolites that can be measured *index cellular energetics* in the form of phospholipid precursors, metabolites, and high energy phosphates. A  $^{31}\text{P}$  MRS scan, for example, can measure the phosphocreatine (**PCr**) and **ATP** (two doublets and a triplet) resonances with their ratio frequently used as a tissue-energy status indicator. Similarly, the phosphomonoester (**PME**) and phosphodiester (**PDE**) peaks represent precursors of membrane synthesis and breakdown products.

Finally, several of our *target metabolites are linked to cellular structure and, as such, are often found to be markers of pathology*. N- Acetyl-Aspartate (**NAA**) in the brain is localized to the neuronal bodies, axons and dendrites and is hence considered a marker for neuronal integrity and function. Studies of disease involving loss of neurons (stroke, epilepsy, tumors, multiple sclerosis) have shown a consistent decrease of NAA. Additionally, the choline peak in the brain consists of Choline (**Cho**), Phosphocholine (**PCho**) and Glycerophosphocholine (**GIPCho**) and reflects cellular density and membrane breakdown.

Our proposed work uses cutting edge techniques to investigate whether effects of BOTOX can be observed in the CNS. The techniques will maximize the number of detectable metabolites by including not only traditional  $^1\text{H}$  MRS, but eventually also including  $^{31}\text{P}$ -based MRS.

## Preliminary Data

[figure not shown]
Our research group has significant experience in a wide range of MRI techniques, including MRS. As we have only recently begun MRS scanning on the 3T Philips magnet at UC Irvine, we present here sample data from this scanner to demonstrate its viability. Demonstrations

## Measuring the effects of BOTOX on the brainstem using MR Spectroscopy (MRS) and fMRI

of functional, structural, and diffusion-based MRI on the UCI scanner are available [in our published work](#) (e.g., Bennett and Stark, 2015, Stark et al. 2015, Mattfield and Stark 2015, Yunshkevich et al. 2015, Huffman and Stark 2014, Lacy et al. 2012).

### Sample 1H MRS data

[figure not shown]
To demonstrate our ability for 1H MRS in the hippocampus, brain stem and posterior cingulate, we have collected pilot data using our 3T Philips MRI in combination with a 32-channel head coil. 1H spectroscopy data were acquired using the PRESS localization sequence (Bottomley, 1984; TR/TE = 2000/37 ms), from a 2.5x1.5x1 cm voxel in the left and right hippocampi of all subjects following an established protocol (Valenzuela et al, 2003). For the posterior cingulate, a larger voxel measuring 2x2x2 cm was selected. Due to its smaller location, the brainstem voxel measured 1.5x1x1 cm All spectra were processed using the TARQUIN software (v.4.3.6) for NMR/MRS spectra quantitation (Wilson et al., 2011) and a sample is shown in Figure 1.

Preliminary 1H MRS results are shown in Figure 2 and are remarkably similar to prior work (Bartha et al., 2008). This measurement is shown in the hippocampus but can be done in any other brain structure, including the brainstem and the posterior cingulate.

### Sample SV-PRESS (1H) data for GABA

[figure not shown]
In addition to the standard metabolites measured with short TE (37ms) PRESS, we now have the capability for improved GABA measurements by choosing the combination of TE1/TE=15/105 ms results in most optimized parameters to resolve the 1.89 and 2.28 ppm peak of the GABA spectrum. We are currently testing and tuning its parameters.

**Fig 2: Our hippocampal SV PRESS (N=9, red) and from Bartha et al. (2008, blue)**

### High resolution fMRI of the Brainstem

Our laboratory routinely collects high resolution fMRI of the medial temporal lobe for memory and aging studies. Coincidentally, our protocol is also ideally oriented to observe fMRI of the brainstem. Initial results with high resolution (1.5mm) fMRI of the brain stem are shown in Figure 3.

**Fig 3. (Left) high resolution fMRI image, before spatial smoothing with corresponding time series (TR=2). On right, high resolution T2 image of brainstem for region of interest registration.**

## Hypotheses

There are two goals of the proposed preliminary work. The first is to determine whether there are metabolic differences in the brain stem in healthy individuals as a result of peripheral administration of BOTOX into the glabellar muscles. This is an open question that can be addressed with MRS. While the doses used in cosmetic treatments are low, an effect via the trigeminal nerve is certainly possible and knowing whether such an effect exists in this cohort would be highly relevant for attempts to understand the effects of BOTOX on disorders such as migraine or depression. Importantly, we proposed to diverge from typical MRS here and to employ “functional MRS” by collecting MRS data during the performance of an emotionally-arousing task. If BOTOX is altering emotional processing in the brain via a “facial feedback” mechanism, altered metabolite levels in the brainstem might be resolved.

The second goal is to better understand the effect of BOTOX on functional activity (measured using fMRI) in the brain and in the brainstem. Consistent with prior work, we propose that BOTOX will alter emotional-related activity in the amygdala (Kim J, 2014). We propose to extend this work in several ways by measuring fMRI activity in the brainstem as well and understanding its relationship to activity in structures such as the amygdala. Again, if BOTOX is altering emotional processing via an alteration of the facial feedback mechanism, this could be resolved either as an alteration of fMRI activity levels or as an alteration in “functional connectivity” (correlation of activity over time) between the brainstem and the amygdala.

## Proposed Protocol: Pilot Study on Healthy Controls

Our aim is to be able to examine the effects of BOTOX on the CNS to determine potential mechanisms for the effects of BOTOX on disorders such as migraine and depression. To date, there are no MRS studies of BOTOX to guide the investigation. We therefore propose a staged design with an initial pilot study in healthy controls undergoing BOTOX treatment for cosmetic purposes, potentially followed by an expanded study in patients being treated for migraine or depression. Additionally, in this initial pilot, we will explore the feasibility of brainstem fMRI in those two groups of participants. The connectivity between regions in the brainstem will be studied in the presence of angry/happy faces paradigm and at rest. Possible connections with metabolite changes will be explored as well.

**Participants:** We propose to scan 10 healthy, right handed females. Because the sample size is so small, we will be constraining the inclusion/exclusion criteria to minimize variability. Participants will be naïve BOTOX users (e.g. no previous use of BOTOX), ages 30-40 years old. Participants will be excluded for the presence of neurological or psychiatric conditions or the presence of any risk factors for MRI. Participants will be recruited from UCI and/or the surrounding community via e-mail blasts and word-of-mouth. They will receive \$50 compensation per MRI scan and the cosmetic BOTOX will be provided by Allergan.

**Design:** We propose a pre- and post-design. One scan will be collected prior to BOTOX injection and the second will be collected 2-4 weeks post-injection. BOTOX injections will be limited to 20 units in the glabellar area, as approved by the FDA and administered by a

## Measuring the effects of BOTOX on the brainstem using MR Spectroscopy (MRS) and fMRI

certified clinician at the UC Irvine Medical Center (ENT Satellite Office in Irvine). Each scanning session will last approximately one hour and include:

- 1) T1 MPRAGE (3D whole-brain structural image) = 5 min
- 2) T2 localizers (axial, coronal and sagittal) = 6 minutes
- 3) Resting state fMRI = 7 minutes
- 4) fMRI (reduced TR and FOV) = 15 min
- 5) MRS–SV of brain stem = 7 min

**MPRAGE:** This is a standard 3D structural image of the whole brain that will allow us to localize all fMRI findings as well as to determine whether there are any pre-existing cortical abnormalities in any participants. While we do not expect to observe any pre- vs. post-structural changes regional brain shape or size, we will be able to assess these factors.

**Resting-state fMRI:** We will collect whole-brain fMRI data for 7 min of eyes-open resting state fMRI. This data is commonly used to reveal patterns of network-level connectivity (and group-level changes in connectivity) in the brain (Power et al., 2011). Changes in resting states between groups (with and without BOTOX) would likely be observed. We will examine the frequency of switching of modes (unique waveforms from multi-component analysis) between groups. We will also explore the functional connectivity between dura-sensitive neurons and their projections to the hypothalamus, thalamus and mid-brain, as shown by Burstein (Burstein et al., 1998).

**fMRI:** The volunteers will participate in an fMRI scanning session following the protocol of Kim et al. 2014. Photos of series of angry, happy and surprised facial expressions (consisting of 9 male and 9 female identities) will be presented for 17, 50 and 1000 ms followed by black and white pattern, presented for 250 ms (serving as a retinal wipe). During each trial, participants will be asked to report using a button box whether they thought each of the faces they saw represent a positive or a negative emotion. We will analyze fMRI data of the brainstem following a modified method used by Beissner et al. 2011.

**MRS-1H** This will serve as an exploratory study to quantify a series of standard metabolites (described above) from a voxel located in the brainstem. If BOTOX injections invoke plasticity in the afferent motor pathways, the MRS data acquired may detect altered Glutamate or GABA concentrations, as GABAergic systems relate to short term motor learning and behavior (Stagg et al. 2011, Floyer-Lea et al. 2006). Differences in metabolite concentrations in brainstem following the fMRI task may show a link between this region and the amygdala, where those activations have been shown to occur (Kim et al. 2014). These concentrations may be further modulated in the presence of BOTOX injection.

### Problems and Alternatives:

Our preliminary data of 1H-MRS of the hippocampus, brainstem and posterior cingulate have yielded results comparable with other published studies. However, the small voxel sizes used in our preliminary data yield spectra with moderate noise. This can be improved by increasing the voxel sizes in line with other literature. Recent advances have provided the means to

Measuring the effects of BOTOX on the brainstem using MR Spectroscopy (MRS) and fMRI

measure hard to resolve peaks (such as GABA) through the use of multi echo PRESS parameter selection should mitigate the need for new and expensive hardware and software.

Additionally, fMRI of the brainstem is not common and some claim it poses some additional difficulty due to increased physiological noise (Beissner et al. 2011). Our high resolution fMRI data of the hippocampus/brainstem do not seem to be suffering from these issues, but it is possible that the thicker slices and larger voxel sizes used in whole brain (standard-resolution) scans will. We will conduct tests on several existing datasets in our lab and others to determine the magnitude of any such effects and will adjust to higher-resolution oblique coronal images (covering the brainstem and amygdala, but potentially eliminating portions of either frontal or occipital cortex) if needed.

Finally, we have not proposed to include  $^{31}\text{P}$  MRS in this initial, pilot study. We are currently developing a  $^{31}\text{P}$  protocol and building the coil that will subsequently be used to acquire the  $^{31}\text{P}$  MRS data. This part of the protocol would be added to the preliminary study provided that the coil is ready in the timeframe for initiation of this project.

1

Measuring the functional effects of BOTOX on the brainstem using MR Spectroscopy (MRS) and fMRI

PI: [name]., Professor

[name] Department of Neurobiology & Behavior University of California, Irvine [name] [contact] [contact]

STATISTICAL ANALYSIS PLAN

MRS Data Analyses

Metabolite FIDs will be averaged within each task and processed using TARQUIN (v.4.3.6) software for spectral fitting. We chose a block design (vs. event-related) for its higher detection efficiency (at the cost of the inability to sort by individual trial performance or estimate HRF shape)⁷⁵. Within-task dynamics will be investigated by a moving average windowing approach. The minimum temporal window will be determined by the SNR. The corresponding binned water unsuppressed spectra will be used as an internal reference for each condition. The acquired MRS spectra will be corrected for tissue type and T2 relaxation differences. Additionally, using TARQUIN we will obtain values for all metabolites mentioned in Preliminary results. These values will be collected to ensure that the changes in Glu and GABA signals are real and not due to a result of some other general effect on the MRS data (e.g., BOLD related change in signal). The water peak amplitude changes will be processed with a custom designed MATLAB script⁵.

Functional MRI Data Analyses

The **functional MRI data** will be pre-processed and analyzed using AFNI (Cox, 1996; afni.nimh.nih.gov) and in-house programs written in Matlab and Python. The fMRI data were first subjected to a traditional general linear model analysis using multiple regression in AFNI (Cox, 1996). The task vectors of interest will be individually modelled for each participant's functional data utilizing a deconvolution approach built into AFNI's 3dDeconvolve (Ward, 2001). 15 tent functions will be used to estimate the hemodynamic response to each condition. The resultant fit coefficients (β coefficients) represent activity versus baseline for each condition of interest at a given time point in each voxel. The sum of the resultant fit coefficients over the bulk of the expected hemodynamic response (3-13.5 seconds after trial onset) will be taken as the model's estimate of the response for each trial type and passed on to group-level analyses. The hypotheses will be primarily tested using the standard linear model. Brain activity for positive and negative emotions pre- and post-BOTOX injection will be compared in a 2x2 ANOVA, with planned comparisons for follow-up.

Resting state data will be detrended using 2nd order Legendre polynomials. The time series will be normalized to have zero mean and unit variance and the motion vectors and first derivatives will be regressed out of the signal. The first 6 principal components of the variance will be computed using CompCor (not including global signal) and regressed out of the signal (Behzadi et al., 2007). The data were then temporally bandpass filtered (0.009 to 0.08 Hz) and TRs with framewise displacement >0.5mm, as well as those one TR before and two TRs after, will be removed.

Structural brain volumes will be calculated on the MP-RAGE for each participant using Freesurfer's automatic software for volumetric measures (FreeSurfer 2016; Fischl et al. 2002). These volumes will then be normalized by dividing by total intracranial volume for each participant. T-tests for pre- vs. post- BOTOX injections can then be examined.

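### Must the SAP name a pre/post test for brainstem Glu/GABA and brainstem-amygdala connectivity, and spell out how the faces task enters its 2x2 ANOVA?

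*SAP*

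**What the plan says.** The Protocol, under Hypotheses, sets two goals. For spectroscopy: "The first is to determine whether there are metabolic differences in the brain stem in healthy individuals" after BOTOX, studied by "collecting MRS data during the performance of an emotionally-arousing task". For fMRI, an effect could appear either as altered activity or as altered brainstem-amygdala connectivity.

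The SAP, under MRS Data Analyses, covers processing: "Metabolite FIDs will be averaged within each task and processed using TARQUIN (v.4.3.6) software for spectral fitting". It adds "Within-task dynamics will be investigated by a moving average windowing approach", a water reference, and tissue and T2 corrections. The remaining metabolites serve as a check: "These values will be collected to ensure that the changes in Glu and GABA signals are real". No pre/post comparison appears in that section.

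Under Functional MRI Data Analyses, the SAP says the hypotheses are tested mainly with a linear model. It gives a 2x2 ANOVA (positive or negative emotion, by before or after injection) and pre/post t-tests for brain volumes. The resting-state paragraph ends with the removal of high-motion time points.

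On the task, the Protocol's pilot-study section says: "The connectivity between regions in the brainstem will be studied in the presence of angry/happy faces paradigm and at rest". The later fMRI paragraph lists angry, happy and surprised faces at 17, 50 and 1000 ms, each rated positive or negative by button press. The MRS-1H paragraph says: "Differences in metabolite concentrations in brainstem following the fMRI task may show a link between this region and the amygdala".

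**The concern.** The SAP gives a pre/post test to volumes, where the Protocol expects no change, and none to the metabolites that form its first goal. Its remark about real changes in Glu and GABA, set against a BOLD-related artefact, can be read as change within a session rather than change after BOTOX. The timing of the spectroscopy is also unclear: during a task (Hypotheses), following the fMRI task (MRS-1H), or one 7-minute acquisition with no task named (the scan list under Design).

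Connectivity looks similar. The Protocol mentions brainstem-amygdala coupling, coupling between brainstem regions, mode switching, and projections to the hypothalamus, thalamus and mid-brain. The SAP tests none of them. The ANOVA does not say where surprised faces or the three durations go.

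If the quantity compared were chosen after seeing the data, a reader could not tell a planned result from a selected one, and a patient study may be built on this pilot.

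**Working it through.** The documents give no significance level, power, SD or sample-size calculation, so there is no figure to reproduce. The check compares passages, with some arithmetic at an assumed two-sided 0.05.

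**1. Is the contrast open?** Under Design, the Protocol sets one scan before injection and one 2-4 weeks after, in a single group of 10. The Resting-state fMRI paragraph contrasts states with and without BOTOX. The MRS-1H paragraph says concentrations may be further altered by the injection. With two sessions per person, a linear model with a participant effect and a session effect is the paired t-test on 9 degrees of freedom. The contrast is therefore settled; the summary measure is not.

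**2. Can the task be reduced to the ANOVA?**
- Task cells: 3 expressions × 3 durations = 9 per session, and 9 × 2 = 18 over two sessions.
- ANOVA cells: 2 × 2 = 4.

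A two-level emotion factor is available either from angry versus happy faces, as the pilot-study section describes the task, or from the positive/negative button response. Durations can be pooled. The SAP estimates each condition separately before the group level, so either reduction is possible. The mapping is unstated rather than contradictory.

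**3. How much of goal 2 is untested?** The Protocol offers activity or connectivity as alternative routes. Activity has the ANOVA; only connectivity lacks a named test.

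**4. What can n=10 show?** Let SD be that of the paired change.
- 95% CI half-width: t(0.975, 9)/√10 = 2.262/3.162 = 0.715 SD.
- Change detectable with 80% power (noncentral t): 0.996 SD.
- Power: 29% at 0.5 SD, 62% at 0.8 SD, 80% at 1.0 SD.

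For a given summary measure, these are the same whether or not the SAP names the test.

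**5. Does the choice of MRS summary matter?** Assume error SD s for a 7-minute average, session-to-session SD t, and noise falling with the square root of scan time. Neither SD is in the documents, and the split into 3.5-minute halves is only for illustration.
- Session difference in the average: 0.996 × √(2(s²+t²)), which is 1.41 s at t=0 and 1.99 s at t=s.
- Session difference in the change between halves: 0.996 × √8 × s = 2.82 s.
- The two are equal when 2(s²+t²) = 8s², that is t = √3 s ≈ 1.7 s.

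The two answer different questions, and which is more precise depends on an unknown ratio. The figures do not show that either choice is wrong.

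**6. What would naming the tests buy?** Naming Glu, GABA, connectivity at rest and in task, and the interaction in amygdala and brainstem gives six tests. If independent at 0.05, the chance of at least one false positive is 1 − 0.95⁶ = 0.265, about 26%. Counting eight connectivity measures from the Protocol gives 1 − 0.95⁸ = 0.337 if independent, and 0.05 if they are perfectly correlated. That range comes from the assumed correlation and the reviewer's count, not from any rule in the plan.

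**The case for a change.** The strongest case for a change is that it would cost a few sentences and no scans, that it concerns the first stated goal, and that pairing alone does not say which quantity is paired. A session difference in level and a session difference in task-evoked change can disagree, and a null result on one is not a null result on the other. The general linear-model sentence does not close the gap, since it sits in the fMRI section and names no spectroscopy outcome.

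Part of this stands. The summary measure is unnamed, and the wording on whether spectroscopy is acquired during or after the task is ambiguous. That ambiguity is milder than it first looks. The Hypotheses section and the SAP both describe data gathered within a task, and the MRS-1H wording may only reflect scan order, since spectroscopy is last on the list.

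What does not stand is the step from missing detail to a faulty analysis. Making one average primary would also be a preference: it would put session level ahead of the task-evoked change that the Protocol's functional spectroscopy may be meant to capture.

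**Conclusion.** No change to the plan follows. The SAP is thin on Glu/GABA and on connectivity, and silent on how surprised faces and durations enter the ANOVA. The design nevertheless fixes a paired before/after comparison, a two-level emotion factor can be formed from the task as described, and the activity half of goal 2 already has a test. An analyst would run the paired comparison and apply a standard correction to voxelwise maps without being told.

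The stakes are limited by what the study is: 10 participants, preliminary aims, spectroscopy labelled exploratory, and no significance level or decision rule. With an interval of about ±0.72 SD on a single contrast, its results can suggest hypotheses for a patient study but cannot settle one, and naming six tests would not alter that.

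This conclusion assumes that results are reported as exploratory, with the summary used made plain. It would not carry over to a confirmatory patient study, whose own plan would have to fix the outcome, summary and contrast in advance.

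### Does the task fMRI model need a change because the SAP names motion correction only for the resting-state data?

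*SAP*

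**What the plan says.** The SAP section on functional MRI opens with a general statement that these data are pre-processed and analysed in AFNI and in-house programs, without listing steps. For the task, "The task vectors of interest will be individually modelled for each" participant by deconvolution, with 15 tent functions per condition. The coefficients from 3 to 13.5 seconds after trial onset are summed as the response, relative to baseline. The SAP adds that "The hypotheses will be primarily tested using the standard linear model", and a 2x2 ANOVA compares positive and negative emotion before and after injection.

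The next paragraph concerns resting-state data. There "the motion vectors and first derivatives will be regressed out of the signal", six CompCor components are removed, and "TRs with framewise displacement >0.5mm, as well as those one TR before and two TRs after, will be removed". None of these steps is named for the task.

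In the Protocol's pilot-study section, the Design paragraph reads "We propose a pre- and post-design", with 10 participants. The scan list gives the task run as "fMRI (reduced TR and FOV) = 15 min". Of the task analysis the Protocol says "We will analyze fMRI data of the brainstem following a modified method", citing a published brainstem technique. Neither document plans to summarise or compare head motion between the two scans.

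**The concern.** The contrast between the two SAP paragraphs is striking. The resting-state data get three explicit defences against motion and physiological noise, while the analysis that carries the main fMRI test gets none by name. In a one-group before-and-after design, a change in movement between scans cannot be separated from an effect of the injection by comparison with controls. The task asks for a button press on each trial, so some movement tied to trials is possible. The brainstem is a stated target, and the Protocol reports a view in the field that imaging there suffers more physiological noise. If the task model really had no motion terms, a session difference could reflect movement, and a reader would have no motion summary with which to judge it. Leaving the number of components or the censoring threshold open also allows those choices to be made after the data are seen. All of this concerns the fMRI goal; the spectroscopy goal is unaffected.

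**Working it through.** The documents state no power, alpha or effect size for the fMRI analysis, so there is no figure of the plan's own to reproduce. The check has four parts.

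**1. What the text settles.** Named motion or noise steps: three for rest, none for the task. Planned motion comparisons between scans: none. But nothing rules such terms out of the task model. The general pre-processing statement covers all the functional data, and calling the task vectors those of interest is consistent with a model that also holds terms of no interest. The finding is that the steps are unspecified, not that they will be left out.

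**2. Which movement could bias the contrast.** Write the signal as y = Xb + m + e, where X holds the tents and baseline terms and m is the motion artefact. Least squares gives an error in b of (X'X)⁻¹X'm, plus noise.

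- If m is unrelated to trial timing, it goes mainly into the baseline and the residual, and the expected error in the tent coefficients is about zero. This holds even if there is more movement at one scan than at the other.
- If m is locked to trials but alike at both scans, it cancels in the before-and-after difference.
- If m is locked to trials and differs between scans, it biases the session effect. To bias the emotion-by-session interaction, the difference must also depend on the expression shown.

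A simulation agrees on the first case. It used 10 participants, 15 tents, a linear baseline and three times as many motion spikes after injection as before, all assumed. With spikes unrelated to trial onset, the session test rejected in 5.0% of 8,000 runs and 6.1% of a further 2,000. Pooled, that is (400 + 122)/10,000 = 5.2%, against a nominal 5%. Trial-locked spikes did produce bias.

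**3. What the size of a bias would be.** For a paired contrast with n = 10 (9 degrees of freedom, two-sided 5%, noncentral t), a trial-locked shift of 0.1, 0.2 or 0.3 SD would give rejection rates of 5.9%, 8.8% or 13.6%. The arithmetic is right, but every shift is assumed. The documents give neither the size nor the direction of any movement change, so these rates do not measure harm in this trial.

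**4. What carrying over the resting-state set would cost or gain.** Inputs: a 15-minute task run (Protocol scan list); a TR of 2 s (the pilot brainstem figure) or 1.5 s (assumed, since the TR is to be reduced); 2, 3 or 9 modelled conditions; 18 regressors (6 motion vectors, 6 derivatives and 6 components, the two sixes for motion being assumed).

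| | TR 1.5 s | TR 2 s |
|---|---|---|
| Volumes | 900/1.5 = 600 | 900/2 = 450 |
| Residual df after 15 × 2, 3, 9 tents | 570, 555, 465 | 420, 405, 315 |
| 18/df | 3.2%, 3.2%, 3.9% | 4.3%, 4.4%, 5.7% |

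If the regressors explained nothing, the first-level standard error would rise by a factor √(df/(df − 18)), from √(570/552) = 1.016 to √(315/297) = 1.030. If they explained 20% of residual variance (assumed), the variance would fall to between 0.80 × 570/552 = 0.826 and 0.80 × 315/297 = 0.848 of its value. Both calculations take the nuisance terms as unrelated to the task terms. That fails for trial-locked movement, the one case with bias: there, regression also removes true signal. Nor do first-level gains pass directly to the ANOVA, whose error includes variation between participants.

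Censoring removes 1 + 1 + 2 = 4 volumes per isolated flagged volume, which is 6 s or 8 s. If 5% of volumes were flagged (assumed), up to 20% would be lost.

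**The case for a change.** The strongest reply is that the SAP spells these steps out for one data type and not for the other, so a reader cannot tell whether they apply to the task. The remedy looks cheap: a few sentences reusing methods already described. With 10 participants and no controls, one unmodelled difference could matter, and the pilot may lead to a study in patients. The cited brainstem method might deal with noise, but its modification is not described.

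Much of this stands. The gap is real, trial-locked movement is possible, and reporting motion per session would help readers.

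The claim that the resting-state rules can simply be copied does not stand. The resting scan is whole-brain, whereas the task run has a reduced field of view and TR. The SAP does not define the CompCor noise region, which may not be covered equally in the task run. A 0.5 mm displacement threshold also means something different over a shorter sampling interval. Reporting displacement by expression would need a rule for assigning volumes to trials whose modelled responses may overlap. On brainstem noise, the same Protocol section says that the laboratory's own high-resolution data appear free of the problem and directs its worry at coarser whole-brain scans. It also plans tests on existing datasets and a change of acquisition if needed.

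**Conclusion.** No change to the plan is called for. No stated rule gives a wrong result: the SAP leaves the nuisance terms of the task model unsaid, and a team that sets out detailed motion handling at rest can be expected to include suitable terms for the task. The bias is confined to trial-locked movement that differs between scans, and its size cannot be derived from the documents. The known cost of the resting-state set is small, at 3.2% to 5.7% of first-level residual degrees of freedom before censoring, but its benefit rests on assumed figures and its exact form for this scan is open to reasonable choice. A motion summary per session would be a useful descriptive addition to the report, not a correction to the analysis. The conclusion assumes that AFNI pre-processing of the task data will include ordinary motion handling. An explicit statement that the task model omits it would reopen the point.
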